3.2 Secondary Endpoints

The secondary endpoints are:

- Peak serum VHH concentration following administration of the initial dose and peak serum VHH concentration following a course of treatment (if systemic absorption is observed).
- Area under the serum VHH concentration versus time curve (AUC) following administration of the initial dose and following a course of treatment (if systemic absorption is observed).
- Induction of serum anti-VHH IgG antibodies (if systemic absorption is observed).

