6.4 Timing of Doses

The study drug administration date and start and stop times must be recorded in the subject's chart and in the case report form (CRF). Capsules are to be self-administered by the subject three times daily and may be taken with meals. The subject will be provided a subject diary by the research clinic to record study drug administration, date, time, and relationship to meals.

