7.4 Study Day 1 – Pre-Treatment and Post-Treatment

- Record concomitant medications
- Vital signs (blood pressure, respiratory rate, heart rate and temperature)
- Prior to first study drug administration (up to 4 hours before):
 - Serum or urine (beta-hCG) pregnancy test for women of childbearing potential. The results of this test must be confirmed negative prior to beginning study drug administration.
 - Collect blood for serum to be stored for baseline pharmacokinetics
 - Collect blood for serum to be stored for baseline anti-drug antibodies
 - Collect urine Drugs of Abuse screen
 - Obtain baseline stool specimen collected by subject (if subject is unable to produce a void, they are still eligible to be admitted to the study)
- Part B only: Supply one-week supply of study drug to subject (except Day 1 first dose)
- Part B only: Instruct subject on self-administration of study drug at home three times daily. The study drug may be taken with meals or liquids. Instruct subject on recording of study drug administration in study drug diary.
- Observe subject self-administer first dose of study drug with 240 mL of water. Subject should be fasting except for water for one hour before and after the first dose only.
- Two hours (± 30 minutes) after administering first dose of study drug:
 Collect blood for serum to be stored for pharmacokinetics
- History and targeted physical exam for assessment and recording of AEs
- Send subject home with stool collection kit for sample to be collected as close as possible to Day 2 before study visit. Time of collection must be recorded.

7.5 Study Day 2

- Record concomitant medications
- Vital signs (blood pressure, respiratory rate, heart rate, and temperature)

- History and targeted physical exam for assessment and recording of AEs.
- Part B only: Review study drug diary with patient and verify study drug compliance with pill count.
- Obtain stool sample collected by subject.
- 24 hours (± 1 hour) after first dose of study drug:
 - Collect blood for serum to be stored for pharmacokinetics
- Part B only: Send subject home with stool collection kit for sample to be collected as close as possible to Day 8 before study visit.

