7.6 Study Week 2 (Study Day 8)

- Record concomitant medications
- Vital signs (blood pressure, respiratory rate, heart rate, and temperature)
- Part B only: Collect blood for serum to be stored for pharmacokinetics
- Part B only: Obtain stool sample collected by subject to ship to laboratory.
- Measure hemoglobin, white blood cell count with differential, platelet count, serum PTT, INR, sodium, potassium, calcium, magnesium, phosphate, creatinine, albumin, aspartate aminotransferase (AST), ALT, alkaline phosphatase, total bilirubin, and eGFR
- History and targeted physical exam for assessment and recording of AEs
- Part B only: Review study drug diary with patient and collect returned dosing container to return to pharmacy for quarantine and to verify pill count
- Part B only: Supply one-week supply of study drug to the subject

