⁷ Hematology, chemistry and coagulation studies only need to be performed if screening blood tests were performed more than 2 weeks prior to baseline visit.

Page 30

Table 4 Schedule of Evaluations Part B

	Screening	Week 1		Week 2	Week 3	Week 4	Week 5	End of Study
		Day 1	Day 2	Day 8	Day 15	Day 28	Day 29	Day 56 ⁸
Informed Consent	Х							
Inclusion/Exclusion Criteria	Х							
Medical/Surgical History, Comorbidities	Х							
Record concomitant medications	Х	Х	Х	х	Х	Х		Х
Pregnancy test ⁹	Х	Х				Х		
Physical Examination	Х							
Vital Signs	Х	Х	Х	Х	Х	Х		Х
Height/Weight	Х							
Collect serum for pharmacokinetics ¹⁰		XX	Х	х		Х	Х	
Collect serum for anti-drug antibodies		Х				Х		Х
Collect blood for hematology ¹¹	Х	X ¹⁴		Х	х	Х		Х
Collect serum for chemistry ¹²	Х	X ¹⁴		Х	Х	Х		Х
Collect blood for coagulation ¹³	Х	X ¹⁴		Х	Х	Х		Х
Collect serum for HBsAg, HCV screen	Х							
Collect serum for HIV screen	Х							
Collect urine for Drugs of Abuse screen	Х							
Obtain stool sample		Х	Х	Х		Х	Х	
Administer study drug (first dose) ¹⁵		Х						
Administer study drug po TID daily for 28 days		Х	Х	Х	Х	Х		
History & targeted physical exam for AEs		Х	Х	Х	Х	Х		Х
Verification of dosing by diary, pill count			Х	Х	Х	Х	Х	

⁸ Follow-up at Day 56 (28 days after last dose of study drug ± 4 days) for assessment of adverse events, and blood sampling, including anti-drug antibody and clinical laboratory studies.

⁹ Serum beta-hCG pregnancy test from women of childbearing potential at screening and end of dosing. Repeat serum or urine pregnancy test on Day 1.

¹⁰ Serum PK before, and 2 hours and 24 hours (Day 2) after administering first dose of study drug (Day 1); Day 8; on last day of study drug (Day 28) and on the day following the last dose of study drug (Day 29). This consists of 6 total samples per subject.

¹¹ Hematology to include hemoglobin, white blood cell count with differential, and platelet count.

¹² Serum chemistry to include sodium, potassium, calcium, magnesium, phosphate, creatinine, albumin, AST, ALT, alkaline phosphatase, total bilirubin, and eGFR.

¹³ Coagulation to include PTT and INR.

¹⁴ Hematology, chemistry and coagulation studies only need to be performed if screening blood tests were performed more than 2 weeks prior to baseline visit.

¹⁵ Two subsequent doses for Day 1 are to be self-administered by subject out of the clinic.

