## Listing 16.2.6.1 PK Serum Sample Collection Times (PK Population)

Cohort/Treatment: Part A: LMN-101 3000mg

Subject ID	Sampling Timepoint	Was PK Sample Collected?	Actual Time (h) 	PK Sample Collection Date and Time (YYYY-MM-DD HH:MM)	Day 1 Study Drug Administration Date and Time (YYYY-MM-DD HH:MM)	Comments
XXX-XXX	Day 1 Pre-dose	Yes	xx.xx	YYYY-MM-DD HH:MM	YYYY-MM-DD HH:MM	
	Day 1 2h Post-dose	Yes	xx.xx	YYYY-MM-DD HH:MM	YYYY-MM-DD HH:MM	
	Day 2	Yes	xx.xx	YYYY-MM-DD HH:MM	YYYY-MM-DD HH:MM	
XXX-XXX	Day 1 Pre-dose	Yes	xx.xx	YYYY-MM-DD HH:MM	YYYY-MM-DD HH:MM	
	Day 1 2h Post-dose	Yes	xx.xx	YYYY-MM-DD HH:MM	YYYY-MM-DD HH:MM	
	Day 2		xx.xx	YYYY-MM-DD HH:MM	YYYY-MM-DD HH:MM	
Etc						

Relative to date and time of study drug administration on Day 1

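### The repeat-dose serum samples in Part B are not tied to a dose, so 'Cmax after Day 1' cannot serve as the peak after a course of treatment

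*Protocol*

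**What the plan says.** A secondary endpoint (Protocol 3.2, repeated in SAP 2.3.2) is "peak serum VHH concentration following a course of treatment", conditional on systemic absorption being observed. The SAP reports it as 'Cmax after Day 1' (mock Table 14.2.1.2 and Listing 16.2.6.3).

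The first-dose samples are timed. Protocol 7.4 asks for blood "Two hours (± 30 minutes) after administering first dose of study drug", after an observed dose, and 7.5 asks for the next sample "24 hours (± 1 hour) after first dose of study drug".

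The repeat-dose samples are not. Section 7.6 (Day 8) says only "Part B only: Collect blood for serum to be stored for pharmacokinetics", and 7.8 (Day 28) and 7.10 (Day 29) are equally bare. Footnote 10 of Table 4 gives "Day 8; on last day of study drug (Day 28) and on the day following the last dose of study drug (Day 29"). Protocol 3.4 and 7.18 and SAP Section 9 also name only the day.

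Dosing is three times daily at home, with or without meals. Under 6.4 the diary is to "record study drug administration, date, time, and relationship to meals", and the same section requires administration times in the CRF. The PK listings, however, express sample time as "Relative to date and time of study drug administration on Day 1".

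**The concern.** A peak concentration is defined by its place in the dosing interval. The plan fixes that place for the first dose and leaves it open for every sample taken under repeat dosing. Two participants with identical exposure can then return very different values because one was bled before a dose and the other two hours after it.

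With 4 active participants per dose level, differences in draw time can be as large as any effect of dose or accumulation. A comparison of the post-course value with the Day 1 2 h value could show a rise or a fall for reasons unrelated to the drug. Absorption or accumulation that appears only on repeat dosing could also be missed.

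**Working it through.** **Counts in the plan.** Part B samples per participant: pre-dose, 2 h, 24 h, Day 8, Day 28 and Day 29 = 6, as footnote 10 states. Doses: 3 × 28 = 84, as Protocol 7.1 states. Once repeat dosing is under way, each participant has one untimed sample on Day 8, one on Day 28 and one the day after dosing ends. There is no post-dose series from which a peak could be read.

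**Chance of matching the Day 1 window.** Assume 8-hourly doses and a draw at a uniformly random time. The 2 h ± 30 min window is 1 h wide, so one sample falls in it with probability 1/8 = 12.5%. For the 4 active participants of a cohort on Day 28:
- at least one in the window: 1 − (7/8)^4 = 41%
- all four in the window: (1/8)^4 = 0.02%

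**Effect of draw time on the level.** The documents give no half-life, time to peak or assay limit, so what follows is an illustration. Assume one compartment, absorption rate ka = 1/h, k = ln 2 / half-life, and unit scaled dose. The level is the sum over all earlier doses at times d:

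C(t) = Σ ka/(ka − k) × [exp(−k(t − d)) − exp(−ka(t − d))]

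Day 28 levels, before the first dose of the day and 2 h after it:

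| Half-life | Doses at 0/6/12 h: pre-dose, 2 h, ratio | Doses every 8 h: pre-dose, 2 h, ratio |
|---|---|---|
| 2 h | 0.027, 0.572, 21 | 0.102, 0.609, 6.0 |
| 4 h | 0.227, 0.852, 3.8 | 0.403, 0.977, 2.4 |
| 8 h | 0.862, 1.497, 1.7 | 1.095, 1.693, 1.55 |
| 12 h | 1.562, 2.193, 1.4 | 1.806, 2.412, 1.3 |

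The largest figure depends on the 12 h overnight gap. Even spacing cuts it from 21 to 6.0.

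**Effect on the Day 28 to Day 1 comparison.** At a 4 h half-life with doses at 0/6/12 h, the Day 1 2 h level is 0.692. A Day 28 draw at 2 h gives 0.852/0.692 = 1.23, which is mild accumulation. A pre-dose draw gives 0.227/0.692 = 0.33, which looks like a threefold fall.

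**Whether the SAP repairs it.** SAP 9.1 counts time from the initial dose, not the latest one. The Section 9 fallback for an unrecorded time is the nominal time, but these visits have no nominal hour. Listing 16.2.5.2 is restricted to the first dose on Day 1. Time since last dose therefore appears in no planned PK output.

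**The case against.** A reader might infer that the trial could wrongly conclude there is no systemic absorption. The documents do not support that. All 14 active participants (2 in Part A, 12 in Part B) have a timed 2 h first-dose sample, and the dataset behind the decision on PK analysis and antibody testing (SAP 15.1) is serum VHH data generally, not Days 8 and 28 alone. In the model above with doses at 0/6/12 h, the Day 1 2 h level is 20.5 times the Day 28 pre-dose level at a 2 h half-life (0.558/0.0273). It is 98% of the Day 28 2 h level (0.558/0.572). So the short half-life that makes a trough hard to detect is the case that the Day 1 sample covers well. What remains is a signal that appears only with repeat dosing.

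A reader might also infer that Day 8 is always an overnight trough. Section 7.4 says "Supply one-week supply of study drug to subject (except Day 1 first dose"), which read literally is 7 × 3 − 1 = 20 doses ending on Day 7, with new drug handed out at the Day 8 visit. That assumes no overage, which the documents do not settle. If true, it would also make Day 8 fairly uniform between participants.

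Other points stand. Time since last dose could be derived from records that 6.4 already requires. The 55 kDa protein is not expected to be absorbed, so the endpoint may never be reported. The Study Manual and the Protocol Clarification Letter cited in the SAP are not available here and might set draw times. None of this puts a timing rule in the protocol or SAP, and dose times derived afterwards cannot create a sample near the peak.

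**Conclusion.** The point holds for the post-course peak endpoint. As written, 'Cmax after Day 1' is the highest of a few levels whose repeat-dose members are untimed. It does not measure the stated endpoint and is not comparable with the Day 1 2 h value, between participants or across dose levels. The possible distortion runs from 1.3-fold to 21-fold over half-lives of 2 to 12 h and the two dose spacings tried. Those figures rest on an assumed one-compartment model with ka = 1/h and on the draw being pre-dose, so they show scale and do not predict. The consequence for the absorption decision is limited to absorption or accumulation seen only on repeat dosing. The conclusion assumes that no document outside the protocol and SAP fixes the draw times.

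**What to change.** - In Protocol 7.6, 7.8 and footnote 10 of Table 4, schedule the existing Day 8 and Day 28 PK draws at 2 h (± 30 min) after a scheduled dose, to match the Day 1 sample. Dose, number of doses and food rules stay as they are.
- Derive time since last dose for the Day 8, 28 and 29 samples from the CRF and diary times under 6.4, and add it to Listings 16.2.6.1 and 16.2.6.2.
- Relabel 'Cmax after Day 1' as 'highest observed post-Day 1 concentration' whether or not the draws are timed. One 2 h sample is comparable with Day 1 but is still not a peak: with doses at 0/6/12 h, the modelled daily maximum is 1.2 to 1.3 times the morning 2 h level.

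Cost: two existing visits may last up to about 2 h longer, plus one derived column in two listings. No visit or blood draw is added. If the samples have already been taken, only the derivation and the relabelling apply.

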7.12 Non-Study Medications

Non-study medications are permitted during this study except for other investigational drugs and those not allowed in the Exclusion Criteria. Any reported non-study medication will be recorded and evaluated by the Investigator. Use of other investigational drugs or drugs prohibited by the study enrollment criteria may be cause for exclusion or discontinuation of a subject (see Exclusion Criteria).

7.13 Study Drug Assignment

Subjects meeting all inclusion and exclusion criteria will be sequentially assigned a randomisation number from a list provided to the designated pharmacist. Pharmacy personnel preparing the study drug for dispensing will be unblinded. The Pharmacist(s) delegated by the PI are responsible for maintaining the randomisation schedule and the name of the subject assigned to that randomisation number.

7.15 Subpopulations for Analysis

Modified Intent-to-Treat Population

The modified intent-to-treat analysis will include all randomised subjects meeting inclusion criteria who receive at least one dose of study drug.

Per-Protocol Subjects

An analysis of the per-protocol population will be performed to include all randomised subjects who complete the full course of study drug and who have data collected for the primary endpoint.

7.16 Data Safety and Monitoring Plan

Investigators are responsible for monitoring the safety of subjects who have entered this study. Subjects will be frequently assessed for AEs by the research nurse and PI, with the latter acting as site medical monitor.

The investigator is responsible for appropriate medical care of subjects during the study. The investigator remains responsible to follow, through an appropriate health care option, AEs that are serious, cause the subject to discontinue before completing the study, or are ongoing at the time of study completion. The investigator will maintain responsibility for forwarding of SAEs to the institutional review board. The subject will be followed until the event resolves or stabilizes. Frequency of follow-up is left to the discretion of the investigator.

7.17 Safety Analysis

The analysis of safety will include all subjects who received study drug. Safety will be evaluated from reported AEs, physical examination findings, vital signs, and clinical laboratory values as described below:

- The incidence and number of all reported AEs and treatment-related AEs will be tabulated by treatment group. AEs will be classified by Organ System Classification.
- AEs and SAEs will be summarized by organ system classification, severity, and relationship to study drug. In the event of multiple occurrences of the same AE with the same preferred term in the same subject, the AE will be reported as the number of AEs and with the AE counted only once. The incidence of AEs will be tabulated by Organ System Class and treatment group.
- AEs indicative of secondary infection will also be compared between treatment groups.

• SAEs will be presented as listings by treatment group. The event, start and stop dates and times, relationship to study drug, severity, and outcome will be presented. Outcomes attributed to SAEs will be tabulated separately by treatment group.

Tolerability will be assessed by the proportion of participants completing study drug and remaining on study and free from possibly drug-related and dose-limiting SAEs to the end of follow-up.

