4.3 Safety Criteria for Stopping Dosing

Advancing to the next dose cohort will be done after review of safety data by the PI and the Sponsor's Medical Monitor, both of whom are unblinded as to treatment assignment in Part A and blinded as to treatment assignment in Part B. If a dose is safe, then the next dose cohort will be enrolled. Criteria that would result in a pause in active dosing and further investigation by the study team include if any subject experiences a SAE deemed related to the study drug; if two or more subjects experience the same grade 3 or higher AE; if accumulation of SAEs and/or AEs collectively raises a safety concern in the opinion of the investigator, research monitor, or study sponsor; or if any subject experiences an adverse event of special interest (AESI).

If a subject develops a significant allergic reaction or anaphylaxis following study drug administration, the study drug will be immediately discontinued for that subject and no further doses given. The PI should contact the Sponsor's Medical Monitor to determine whether to discontinue study treatment for a given subject. Regardless of communication with the Sponsor, the PI is authorized to discontinue the study drug at any time if it is in the best interest of the safety of the subject. Treatment may also be discontinued at the request of the subject.

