7.19 Potential Toxicities

The potential toxicities of LMN-101 are primarily related to the effects associated with monoclonal antibodies (mAbs) in general. As with all drugs and biologics, there is the potential for individual allergic reactions. Considerable human experience has been accumulated with mAb therapy. The adverse effects of treatment with mAbs are diverse and appear to be dependent on the species of origin (murine versus human) and the antigenicity of the antibody. To date, there is no other reported clinical experience with another mAb against campylobacter.

Potential toxicities that may exist with LMN-101 include the formation of antibodies against LMN-101. Since LMN-101 is a protein macromolecule administered orally, systemic absorption is not anticipated so the risk of formation of anti-drug antibodies is low. Please see the Investigator's Brochure for additional information.

Since LMN-101 is a subunit of an antibody and does not contain an Fc domain, there is not a possibility of Fc binding. Since LMN-101 is directed against a bacterial antigen that does not cross-react with human tissue, there is no anticipated non-specific binding to human tissue.

While there is theoretically a remote possibility of a potential effect on the normal gut microbiome, antibodies against the target antigen, FlaA of campylobacter flagellin do not cross react with normal flora of the gut microbiome.

8 ADVERSE EVENTS (AEs)

An AE is the development of an undesirable medical condition or the deterioration of a preexisting medical condition following or during exposure to a pharmaceutical product, whether considered caused by the product or not. In clinical studies, an AE can include an undesirable medical condition occurring at any time, including baseline or washout periods, even if no study treatment has been administered.

All AEs that occur after any subject has been enrolled, before treatment, during treatment, or within days following the cessation of treatment, whether they are related to the study or not, must be recorded on forms provided by Lumen Bioscience or its representative. Lumen Bioscience and the investigators must abide by the Australian Health Ethics Committee statement "Safety monitoring and reporting in clinical trials involving therapeutic goods." http://health.act.gov.au/sites/default/files//REGO/28.%20AHEC%20Position%20Statement%20 -%20Safety%20Reporting%20-%20November%202016.pdf

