### **12.1 Adverse Events**

#### **12.1.1 Endpoints**

- AE
- SAE
- TEAE

AEs and SAEs are defined in the study protocol. TEAEs are defined as adverse events that occurred or worsened following the first administration of study medication.

All AEs will be coded using MedDRA. AE summaries will be restricted to TEAEs only.

Summary tables will include the number of participants (%) experiencing an event and the number of events. Participants will be counted only once at each SOC and PT level of summary.

The TEAE summaries will include:

- Overall Summary of TEAEs
  - Number of TEAEs
  - Number of TEAEs with Toxicity  $\geq$  Grade 3
  - Number of Serious TEAEs
  - Number of Study Drug Related TEAEs (Drug Related: A Possibly or Probably related TEAE)
  - Number of TEAEs leading to study withdrawal
- TEAE and SAE summary by SOC and PT
  - TEAEs
  - Treatment Emergent SAEs
  - TEAE by relationship to Study Drug
  - TEAE summary by Toxicity Grade

All AEs will be listed and will include verbatim term, PT, SOC, treatment group, relationship to study drug, toxicity grade, seriousness, reason for serious event, outcome, and action taken with regards to the study drug and AE. Separate listings will be created for SAEs and events leading to study drug withdrawal.

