#### **14. CHANGES TO THE PLANNED ANALYSIS**

No changes to the biostatistical methods planned in the protocol were made.

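### Protocol 7.17 plans a between-group comparison of adverse events indicating secondary infection, but the SAP has no output for it and declares no change

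*Protocol*

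**What the plan says.** Protocol 7.17 (Safety Analysis) asks for AEs to be tabulated by organ class, severity, relationship and treatment group. A further bullet then states: "AEs indicative of secondary infection will also be compared between treatment groups". Neither document defines secondary infection or lists the terms that would indicate it.

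SAP 12.1.1 plans an overall summary of treatment-emergent AEs (TEAEs) and a block headed "TEAE and SAE summary by SOC and PT", which covers all TEAEs, serious TEAEs, relationship and toxicity grade. The counting rule is: "Participants will be counted only once at each SOC and PT level of summary". The SAP table list (section 17) and the mock shells turn this into Tables 14.3.3.1 to 14.3.3.5.

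SAP section 14 states: "No changes to the biostatistical methods planned in the protocol were made".

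On allergy, Protocol 7.19 says: "As with all drugs and biologics, there is the potential for individual allergic reactions". Protocol 4.3 deals with what happens to an individual who has a significant reaction. Neither section asks for a table of allergic events.

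**The concern.** The word 'also' in Protocol 7.17 makes the infection comparison additional to the organ-class tables, so producing those tables does not by itself meet the commitment. Under SAP 15.2 the final analysis follows the SAP, and under SAP section 1 analyses outside it are labelled post hoc. A comparison planned in the protocol would then either not appear or be reported as unplanned, while section 14 tells the reader that nothing changed.

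Safety is the primary endpoint and no test is planned, so readers will judge safety from counts of affected participants. If related events are spread over several rows, those rows do not show how many people are involved.

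**Working it through.** **1. The plan's own figures.** Part A has 2 participants. Part B has three cohorts, each with 4 active and 2 placebo (Protocol 4.1, SAP 2.1). Total: 2 + 3 × (4 + 2) = 20, as stated. Part B active: 3 × 4 = 12. Part B placebo: 3 × 2 = 6. The documents give no event rate, power or detectable difference for infection events, so no further figure can be reproduced.

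**2. Protocol commitment against SAP output.**

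| SAP table | Content | Row or grouping for secondary infection |
|---|---|---|
| 14.3.3.1 | Overall: any, grade 3 or higher, serious, drug-related, leading to drug withdrawal | None |
| 14.3.3.2 | All TEAEs by SOC and PT | None |
| 14.3.3.3 | Serious TEAEs by SOC and PT | None |
| 14.3.3.4 | By toxicity grade, SOC and PT | None |
| 14.3.3.5 | By relationship, SOC and PT | None |

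Result: 0 of 5.

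**3. What the PT rows can show.** Suppose k related PT rows each show one participant in a group of size n. The number of distinct participants is at least 1 (the same person in every row) and at most min(k, n) (a different person in each row). For k = 3:

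| Group | n | Fewest | Most |
|---|---|---|---|
| One active dose | 4 | 1/4 = 25.0% | 3/4 = 75.0% |
| Part B placebo, pooled | 6 | 1/6 = 16.7% | 3/6 = 50.0% |
| Part B active, pooled | 12 | 1/12 = 8.3% | 3/12 = 25.0% |

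These limits use the PT rows alone. The row for any TEAE, or a shared SOC row, can narrow them. A SOC row gives the exact count only if every relevant term falls in that SOC and nothing else does. Even a row for all infections would not separate secondary ones.

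**4. What an added row would not do.** It adds no sample size. With 0 of 12 active participants affected, the two-sided 95% exact upper limit is 1 − 0.025^(1/12) = 26.5%. The row restores a planned display and does not make the comparison precise.

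**The case against.** The strongest reply is that nothing of substance is lost. The analysis is wholly descriptive (SAP 3 and 3.3), so comparing groups can only mean showing counts side by side, and Tables 14.3.3.2 to 14.3.3.5 do that for every term. Listing 16.2.7.1 gives each AE with its SOC, PT and grade under a treatment heading, so the count can be made by hand in 20 people. SAP section 14 speaks of biostatistical methods, and it can be argued that leaving out an undefined subset of AEs is not a change of method.

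Much of this stands, and it keeps the point small. It does not close the gap. A hand count needs a term list, and with none fixed beforehand the choice of terms would be made with treatment known. Whatever section 14 means by methods, a reader will take it to say that Protocol 7.17 has been carried over in full.

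Two stronger readings are tempting, and the documents support neither. The first is that the SAP gives no participant-level count of infection or allergic events. It does: the shells show n (%) and the number of events for every SOC and PT, and only the pooled count across terms is missing. The second is that the SAP breaks a promise on allergic reactions. Protocol 7.19 makes a general remark that applies to any drug or biologic, and the allergy text in Protocol 4.3 is a conduct rule. Neither commits to a tabulation. A treatment-stopping reaction would also appear in the drug-withdrawal row and Listing 16.2.7.3, though mixed with other causes.

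**Conclusion.** The point holds for secondary infection: Protocol 7.17 plans a comparison, no SAP output delivers it, and SAP section 14 does not disclose the omission. This follows from the text and needs no assumption about event rates. The 1-to-3-of-4 example is hypothetical. It assumes only that the relevant events fall under more than one preferred term, and it makes no claim about which terms or organ classes those would be.

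The importance is minor. No figure in the plan is wrong, the data needed are already collected, and the listings allow recovery. What is missing is a definition fixed in advance and one pooled count per treatment group. For allergic events, an added row would be an improvement and not the repair of a broken commitment.

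**What to change.** Add one row to Table 14.3.3.1 for participants with at least one TEAE indicative of secondary infection. Show n (%) and number of events by treatment group, as in the existing rows, and count each participant once.

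State in SAP 12.1.1 what the category means and attach the list of preferred terms. The participants are healthy volunteers, so the definition should say what the infection would be secondary to. Fix the list before database lock, with reviewers blinded to Part B treatment. The SAP has to specify that blinding itself: the pre-lock deviation review in SAP section 6 is not described as blinded, and Protocol 4.3 has the Medical Monitor unblinded in Part A and blinded in Part B. Part A is open-label with 2 participants, so blinding does not arise there.

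If the sponsor prefers to drop the comparison, record that and the reason in SAP section 14. A parallel row for allergic or hypersensitivity TEAEs, built the same way, is optional.

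The cost is one table row (two with the option), a short term list and a sentence or two in the SAP. No new data are needed, and nothing changes in the conduct of the trial.
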